### 5.4 Management of Clinical Events

- Erythematous Rash With or Without Pruritus Rash with or without pruritus has been reported with ixazomib, primarily at the higher doses tested and when given with agents where rash is an overlapping toxicity. The rash may range from limited erythematous areas, macular and/or small papular bumps that may or may not be pruritic over a few areas of the body, to a more generalized eruption that is predominately on the trunk or extremities. Rash has been most commonly characterized as maculopapular or macular. To date, when it does occur, rash is most commonly reported within the first 3 cycles of therapy. The rash is often transient, self-limiting, and is typically Grade 1 to 2 in severity.
  - Symptomatic measures such as antihistamines or corticosteroids (oral or topical) have been successfully used to manage rash and have been used prophylactically in subsequent cycles. The use of a topical, IV, or oral steroid (eg, prednisone  $\leq 10$  mg per day or equivalent) is permitted.
  - Management of a Grade 3 rash may require intravenous antihistamines or corticosteroids. Administration of ixazomib (and/or other causative agent if given in combination) should be modified per protocol and re-initiated at a reduced level from where rash was noted
  - In line with clinical practice, a dermatology consult that include a biopsy of Grade 3 or higher rash or any SAE involving rash is recommended. Prophylactic measures should also be considered if a patient has previously

developed a rash (eg, using a thick, alcohol-free emollient cream on dry areas of the body or oral or topical antihistamines).

- A rare risk is Stevens-Johnson Syndrome, a severe and potentially lifethreatening rash with skin peeling and mouth sores, should be managed symptomatically according to standard medical practice. Punch biopsies for histopathological analysis are encouraged at the discretion of the investigator.
- **Thrombocytopenia.** Blood counts will be monitored regularly as outlined in the protocol with additional testing obtained according to standard clinical practice. Thrombocytopenia may be severe but has been manageable with platelet transfusions according to standard clinical practice. Ixazomib administration should be modified as noted as per dose modification recommendations in the protocol when thrombocytopenia occurs (see Section 6.1). Therapy can be reinitiated at a reduced level upon recovery of platelet counts. A rare risk is thrombotic thrombocytopenic purpura (TTP), a rare blood disorder where blood clots form in small blood vessels throughout the body characterized by thrombocytopenia, petechiae, fever, or possibly more serious signs and symptoms. TTP should be managed symptomatically according to standard medical practice.
- **Neutropenia.** Blood counts will be monitored regularly as outlined in the protocol with additional testing obtained according to standard clinical practice. Neutropenia may be severe but has been manageable. Growth factor support is not required but may be considered according to standard clinical practice. Ixazomib administration should be modified as noted as per dose modification recommendations in the protocol when neutropenia occurs (see Section 6.1). Therapy can be reinitiated at a reduced level upon recovery of ANCs.
- Fluid Deficit. Dehydration should be avoided since ixazomib may cause vomiting, diarrhea, and dehydration. Acute renal failure has been reported in patients treated with ixazomib, commonly in the setting of the previously noted gastrointestinal toxicities and dehydration.
  - Fluid deficit should be corrected before initiation of study drug and as needed during treatment to avoid dehydration.
- **Hypotension.** Symptomatic hypotension and orthostatic hypotension with or without syncope have been reported with ixazomib. Blood pressure should be closely monitored while the patient is on study treatment and fluid deficit should be corrected as needed, especially in the setting of concomitant symptoms such as nausea, vomiting, diarrhea, or anorexia. Patients taking medications and/or diuretics to manage their blood pressure (for either hypo- or hypertension) should be managed according to standard clinical practice, including considerations for dose adjustments of their concomitant medications during the course of the trial. Fluid deficit should be corrected before initiation of study drug and as needed during treatment to avoid dehydration.

- **Posterior Reversible Encephalopathy Syndrome.** One case of posterior reversible encephalopathy syndrome, which ultimately resolved, has been reported with ixazomib. This condition is characterized by headache, seizures and visual loss, as well as abrupt increase in blood pressure. Diagnosis may be confirmed by magnetic resonance imaging (MRI). If the syndrome is diagnosed or suspected, symptom-directed treatment should be maintained until the condition is reversed by control of hypertension or other instigating factors.
- **Transverse Myelitis.** Transverse myelitis has also been reported with ixazomib. It is not known if ixazomib causes transverse myelitis; however, because it happened to a patient receiving ixazomib, the possibility that ixazomib may have contributed to transverse myelitis cannot be excluded.
- **Pregnancy.** It is not known what effects ixazomib has on human pregnancy or development of the embryo or fetus. Therefore, female patients participating in this study should avoid becoming pregnant, and male patients should avoid impregnating a female partner. Nonsterilized female patients of reproductive age group and male patients should use effective methods of contraception through defined periods during and after study treatment as specified below.
  - Female patients must meet 1 of the following:
    - Postmenopausal for at least 1 year before the screening visit, or
    - Surgically sterile, or
    - If they are of childbearing potential, agree to practice 2 effective methods of contraception from the time of signing of the informed consent form through 90 days after the last dose of study drug, or
    - Agree to practice true abstinence, when this is in line with the preferred and usual lifestyle of the subject. (Periodic abstinence [eg, calendar, ovulation, symptothermal, postovulation methods] and withdrawal are not acceptable methods of contraception.)
  - Male patients, even if surgically sterilized (ie, status postvasectomy) must agree to 1 of the following:
    - Practice effective barrier contraception during the entire study treatment period and through 90 days after the last dose of study drug, or
    - Agree to practice true abstinence, when this is in line with the preferred and usual lifestyle of the subject. (Periodic abstinence [eg, calendar, ovulation, symptothermal, postovulation methods for the female partner] and withdrawal are not acceptable methods of contraception.)

#### 5.5 Criteria for Taking a Participant Off Protocol Therapy

Patients will be informed that they have the right to withdraw from the study at any time for any reason, without prejudice to their medical care.

In the absence of treatment delays due to adverse event(s), treatment may continue for 24 cycles or until one of the following criteria applies:

- Progression to overt Multiple Myeloma
- Intercurrent illness that prevents further administration of treatment
- Unacceptable adverse event(s)
- Participant demonstrates an inability or unwillingness to comply with the oral medication regimen and/or documentation requirements
- Participant decides to withdraw from the protocol therapy
- General or specific changes in the participant's condition render the participant unacceptable for further treatment in the judgment of the treating investigator

Participants will be removed from the protocol therapy when any of these criteria apply. The reason for removal from protocol therapy, and the date the participant was removed, must be documented in the case report form (CRF). Alternative care options will be discussed with the participant.

When a participant is removed from protocol therapy and/or is off of the study, the relevant Off-Treatment/Off-Study information will be updated in OnCore.

In the event of unusual or life-threatening complications, treating investigators must immediately notify the Overall PI,

#### 5.6 Duration of Follow Up

Participants will be followed for **3 years** after removal from protocol therapy or until progression to active symptomatic MM, whichever occurs first. Participants removed from protocol therapy for unacceptable adverse event(s) will be followed until resolution or stabilization of the adverse event.

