#### **1.6 Secondary Objectives**

- To assess the response rate of the combination in these patients
- To assess time to progression and progression free survival
- To assess duration of response
- To assess safety of the combination
- To examine molecular evolution of the tumor cells obtained

CONFIDENTIAL

This document is confidential. Do not disclose or use except as authorized.

• To determine minimal residual disease (MRD)

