#### 2.6 Treatment of High-Risk SMM

In a randomized open-label phase 3 trial , 119 patients with high-risk smoldering myeloma were randomized to treatment or observation. Patients in the treatment group received an induction regimen (lenalidomide at a dose of 25 mg per day on days 1 to 21, plus dexamethasone at a dose of 20 mg per day on days 1 to 4 and days 12 to 15, at 4-week intervals for nine cycles), followed by a maintenance regimen (lenalidomide at a dose of 10 mg per day on days 1 to 21 of each 28-day cycle for 2 years). The primary end point was time to progression to symptomatic disease. Secondary end points were response rate, overall survival, and safety. After a median follow-up of 40 months, the median time to progression was significantly longer in the treatment group than in the observation group (median not reached vs. 21 months; hazard ratio for progression, 0.18; 95% confidence interval [CI], 0.09 to 0.32; P < 0.001). The 3-year survival rate was also higher in

CONFIDENTIAL

This document is confidential. Do not disclose or use except as authorized.

the treatment group (94% vs. 80%; hazard ratio for death, 0.31; 95% CI, 0.10 to 0.91; P=0.03). A partial response or better was achieved in 79% of patients in the treatment group after the induction phase and in 90% during the maintenance phase. Toxic effects were mainly grade 2 or lower. Early treatment for patients with high-risk smoldering myeloma delays progression to active disease and increases overall survival. (NCT00480363).

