#### 5.7 Criteria for Taking a Participant Off Study

Participants will be removed from study when any of the following criteria apply:

- Lost to follow-up
- Withdrawal of consent for data submission
- Death

The reason for taking a participant off study, and the date the participant was removed, must be documented in the case report form (CRF). In addition, the study team will ensure Off Treatment/Off Study information is updated in OnCore in accordance with DF/HCC policy REGIST-101.

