### **13. STATISTICAL CONSIDERATIONS**

### **13.1 Study Design/Endpoints**

The primary endpoint of this phase II study is to determine the proportion of patients with high-risk smoldering multiple myeloma (SMM) patients who are progressive free at 2 years after receiving therapy with Ixazomib/lenalidomide and dexamethasone. The secondary objectives include toxicities, objective response rate, time to progression, duration of response, and overall survival.

The proportion of patients who achieve progression free at 2 years will be compared to the rate published for the high-risk SMM. By the Mayo Clinic model for risk factors, the median time to progression for patients with high-risk SMM was only 1.9 years. Therefore, a 2-year progression-free rate of 50% will not be considered promising. We assume that the true 2-year progression-free rate is 70%. With a type I error of 5% and power of 90%, 53 eligible patients will be required in a single-stage design. The probability of concluding that the treatment is effective if the true rate is 50% is 0.05 and is 0.91 if the true rate is 70%. Assuming an ineligibility rate of 5%, we will accrue 56 patients to the trial in order to have 53 eligible patients. Any patients who are registered, but do not start study treatment will be replaced.

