### 13.1.2 Analysis of Secondary Endpoints

The objective response rate (partial response or better according to the modified IMWG criteria) and the proportion of patients with a MRD, CR, PR or MR will be reported with 90% exact binominal confidence interval (CI).

To estimate the duration of response (time from objective response to disease progression or death, or date last known progression-free and alive for those who have not progressed or died), progression-free survival (time from protocol therapy initiation to the disease progression or death from any cause, censored at date last known progression free for those who have not progressed or died), and overall survival (time from protocol therapy initiation to death or date last known alive), the Kaplan-Meier method will be used.

Safety analysis will be conducted using the Safety Population defined as any patient receiving one dose of study treatment. For toxicity reporting, all adverse events and laboratory abnormalities will be graded and analyzed using CTCAE version 4 as appropriate.

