### 13.2 Sample Size, Accrual Rate and Study Duration

A total of 56 patients will be enrolled. Any patients who are registered but do not start study treatment will be replaced. We expect 1.5 years of active accrual (approximately 2 patients per month) and 3 years of follow-up of patients.

The final analyses of progression-based endpoints, such as estimating the 2-year progression-free rate and estimating the TTP distribution, will be conducted at the end of the study, which will occur after either all subjects have progressed or died or 3-years after the initiation of therapy of the last subject enrolled, whichever occurs first.

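### Overall survival is a planned Kaplan-Meier secondary endpoint, but follow-up stops at progression and no visible text schedules vital-status contact afterwards

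*Combined protocol and SAP*

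**What the plan says.** Section 13.1 states: "The secondary objectives include toxicities, objective response rate, time to progression, duration of response, and overall survival". Section 13.1.2 gives the definition and method: "overall survival (time from protocol therapy initiation to death or date last known alive), the Kaplan-Meier method will be used". The lists in the Protocol Summary and section 1.6 do not include overall survival; the nearest entry in 1.6 is "To assess time to progression and progression free survival".

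Section 5.6 sets follow-up at three years "after removal from protocol therapy or until progression to active symptomatic MM, whichever occurs first". Section 5.7 gives three reasons for coming off study: loss to follow-up, withdrawal of consent for data submission, and death. Progression is not one of them. It adds: "The reason for taking a participant off study, and the date the participant was removed, must be documented in the case report form (CRF").

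The Event Monitoring column of the Study Calendar (section 10) runs every 3 months, or every 6 at the PI's discretion (footnote 13). It holds examination and laboratory disease assessments, with no survival-status row. Section 7.4.1 covers serious adverse events to 30 days after the last dose. Section 7.6 adds later related events, and new primary malignancies for at least three years after the last dose.

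Section 13.2 times "The final analyses of progression-based endpoints, such as estimating the 2-year progression-free rate and estimating the TTP distribution" at the end of the study. That point is reached when all subjects have progressed or died, or three years after the last subject starts therapy, whichever is first. Section 14 refers back to this definition.

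**The concern.** An overall survival curve needs each patient's death date, or a recent date on which the patient was known to be alive. Here the scheduled source of that information stops at progression to symptomatic myeloma, the point after which mortality may well be higher. If nothing is learned afterwards, progressors are censored near progression. That censoring is informative, and the curve is too high. If deaths happen to reach the case report form but living progressors are not contacted, the living leave the risk set early while the dead count as events, and the curve is too low. The mix would depend on site practice, and the analyst could not undo it without collecting vital status retrospectively.

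Section 2.6 cites a survival difference for early treatment, "the treatment group (94% vs. 80%; hazard ratio for death, 0.31; 95% CI, 0.10 to 0.91; P=0.03"), so a survival curve from this trial would invite comparison with it.

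**Working it through.** **Plan's own figure.** The plan gives no figure for overall survival. Its design figures concern the primary endpoint and reproduce: 33 or more of 53 gives exact one-sided alpha 0.0492 and power 0.914, and 53/0.95 = 55.8, so 56. None depends on post-progression survival.

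**Inputs from the documents.** Progression-free at 2 years: 70% (alternative in 13.1), and 87% from section 2.6 ("median not reached vs. 21 months; hazard ratio for progression, 0.18; 95% confidence interval [CI], 0.09 to 0.32"): exp(-24 x 0.18 x ln2/21) = 0.867. Reported 3-year survival in the cited trial: 80% observation, 94% treatment. N = 56.

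**Assumptions.** Constant hazards, and 2% death without progression by 2 years (varied below). The documents state no post-progression mortality, so it is set to reproduce 80% or 94%.

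**Model (months).** lp = -ln(progression-free rate)/24; ld = -ln(0.98)/24 = 0.000842; a = lp + ld; mu = post-progression hazard.

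- True survival: S(36) = exp(-36a) + lp x [exp(-36mu) - exp(-36a)]/(a - mu)
- Kaplan-Meier limit with every progressor censored at progression: exp(-36 x ld) = 0.970

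Calibrating to 80% (hazard ln2/21) gives a post-progression median of 46.7 months. Calibrating to 94% (hazard 0.18 x ln2/21) gives 65.7 months.

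Example at 70% with median 65.7: lp = 0.01486, a = 0.01570, mu = 0.01056. S(36) = 0.5682 + 0.01486 x (0.6838 - 0.5682)/(0.01570 - 0.01056) = 0.902. Error: 97.0 - 90.2 = +6.8 points.

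**Error in 3-year survival, in points.** Each pair is calibrated to 80% / 94%.

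| Capture after progression | 70% progression-free | 87% progression-free |
|---|---|---|
| True 3-year survival | 87.7% / 90.2% | 93.0% / 94.1% |
| None (upper bound) | +9.3 / +6.8 | +4.1 / +2.9 |
| Half of progressors fully followed (simulated) | +3.9 / +2.9 | +1.9 / +1.4 |
| Deaths only, living progressors censored at progression (simulated) | -2.6 to -2.3 | -0.6 to -0.5 |
| Full capture | 0 | 0 |

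Sensitivity with no capture, recalibrated:

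- 1% death without progression by 2 years: +10.1 at 70% and +4.4 at 87%.
- 4%, calibrated to the observation arm: +7.7 and +3.3.
- 4%, calibrated to the treatment arm: about +0.1 in both.

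Cross-check with different assumptions (annual mortality 0.5-2% before and 5-20% after progression, 70% progression-free): true 3-year survival 85-96%, against 94-98.5% with censoring at progression. The overstatement is about 2 to 11 points.

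**Patients concerned.** Expected number progressed by 36 months after the last start is 56 x the mean of (lp/a)(1 - exp(-a x u)), with u uniform from 36 to 36 + A. Accrual A is 18 months (13.2) or 56/2 = 28 months (at 2 per month). Result: 26.8 to 28.6 at 70%, and 12.6 to 13.8 at 87%.

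**The case against.** The strongest reply is that the sections fit together. Section 5.6 says how long patients are followed and 5.7 says when they leave the study, so both apply. A progressor stays on study until death, loss or withdrawal of consent, and a death is recorded with its date. Section 13.1.2 censors only at the last date known alive, never at progression as such. The malignancy duty in 7.6 has no exemption for progressors and is hard to meet without some news of them. The schema figure and the case report forms are not available here.

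Most of this stands. It shows that a known death can be entered, and that the written definition of overall survival is sound. It does not supply the missing step: 5.7 and 7.6 set no interval, contact or vital-status item, so last-alive dates need not advance after progression.

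Three stronger readings are not supported:

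- **That overall survival has no data cut-off.** Section 13.2 dates the end of the study itself and section 14 refers to it. That date can serve; it is simply not named for overall survival.
- **That progressors leave the study.** Section 5.7 does not list progression.
- **That survival will be overstated by 7 to 9 points.** That needs no deaths captured after progression, although 5.7 allows them to be recorded, plus assumed mortality from one trial's point estimates.

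Precision also limits the weight. With 56 patients, the approximate 95% half-width is 1.96 x sqrt(0.90 x 0.10/56) = 7.9 points at 90% survival and 6.2 at 94%. The upper-bound error at 87% progression-free (2.9 to 4.1 points, about 2 patients of 56) lies inside that. At 70% it is 4 to 5 patients.

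**Conclusion.** The point holds as a minor one. The follow-up rule in 5.6 does not support the overall survival analysis in 13.1.2, and the other sections only partly fill the gap. For 2-year progression-free rates of 70% to 87%, the error in 3-year survival runs from about +10 points through about zero to about -2.6. The sign depends on what sites happen to capture, and the size on mortality that the documents do not give. The error is zero with full capture, or if mortality is the same before and after progression.

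Overall survival here has no hypothesis, comparator or decision attached to it, and a 3-year estimate is used only as a convenient yardstick. Time to progression, progression-free survival and duration of response need no information after progression, and the sample size rests on the primary endpoint alone.

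**What to change.** Amend 5.6 so that disease assessments may stop at progression, while vital status (alive or dead, with date) is collected by telephone or chart check. Do this for all treated patients, at the existing 3- to 6-month interval, until the end of study defined in 13.2. Add a survival-status row to the Study Calendar, name the end-of-study date as the overall survival cut-off, and list overall survival in 1.6. The alternative is to remove overall survival from 13.1 and 13.1.2.

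The cost is brief contacts for about 13 to 29 of 56 patients who will have progressed, plus any non-progressors whose three-year window in 5.6 closes before the cut-off. The latter are mainly early enrollees who stop therapy early. For example, the first patient enrolled, if stopping at month 3, is followed to month 39, while with 18-month accrual the cut-off is at month 36 + 18 = 54. No new visits or procedures are needed.

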#### 5.7 Criteria for Taking a Participant Off Study

Participants will be removed from study when any of the following criteria apply:

- Lost to follow-up
- Withdrawal of consent for data submission
- Death

The reason for taking a participant off study, and the date the participant was removed, must be documented in the case report form (CRF). In addition, the study team will ensure Off Treatment/Off Study information is updated in OnCore in accordance with DF/HCC policy REGIST-101.

